COVER PAGE

Official title of the study: Efficacy of Gluma desensitizer in controlling the immediate post treatment sensitivity in etch-and-rinse and self-etch adhesive occlusal composite restorations

NCT04248803

Date of the document: 02-09-2025

Efficacy of Gluma desensitizer in controlling the immediate post treatment sensitivity in etch-and-rinse and self-etch adhesive occlusal composite restorations

NCT04248803

BRIEF SUMMARY

Background

One of the most widely used esthetic restorations in dentistry is composite. Despite the indispensable value that composite brings to a dentist's arsenal, the postoperative sensitivity following composite resin restorations are an undesirable outcome often leading to patient discomfort.

GLUMA desensitizer, a solution containing glutaraldehyde and hydroxyethyl methacrylate (HEMA), is widely used to reduce sensitivity by occluding dentinal tubules and stabilizing collagen fibrils. However, the ideal timing of GLUMA application in different adhesive protocols remains uncertain, raising questions about its effect on postoperative sensitivity, adhesive bond strength, and long-term restoration success.

This clinical trial aims to evaluate the effectiveness of GLUMA in controlling the immediate post treatment sensitivity following occlusal composite restorations. In addition, to compare the difference between the bonding systems (Etch-and-rinse & Self-etch) on reduction of post restoration sensitivity with or without Gluma desensitizer.

Sample Size, Blinding and Randomization

For this clinical trial, a sample size of 504 restorations was calculated to be sufficient for detecting statistical difference using G* power software (α probability error – 0.05 and effect size – 0.2).

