In this single-blinded clinical trial, the numbers of arms were randomly assigned to six groups. The participants of the study were informed about the trial but were unaware of which treatment group they were allocated to. The clinician and researcher were aware of the groups and treatments given. All patients were allocated using Block randomization. It works by dividing participants into individual blocks and then randomly assigning treatments within each block, ensuring roughly equal numbers in each group within that block. In this clinical trial, a block size of 6 (1, 2, 3, 4, 5, 6) was employed for equal enrolment. The prepared blocks were printed in sheets and patients who met the eligibility criteria were systematically assigned in a continuous fashion. After every 6th patient, the enrolment would continue on to the next block from 1.

Arms (n=84 in each)

Arm 1: Total Etch Control group (No desensitizer application)

Arm 2: Total Etch Gluma prior to acid etchant usage

Arm 3: Total Etch Gluma desensitizer application after acid etchant usage

Arm 4: Self Etch Control group (No desensitizer application)

Arm 5: Self Etch Gluma desensitizer application prior to etching

Arm 6: Self Etch Gluma desensitizer application after self-etch adhesive usage

Materials and Methodology

Caries excavation was done using diamond burs (Mani Co., Tochigi, Japan) with water coolant. Cavity extent was until sound hard or firm discolored or non-discolored dentin was achieved. This was cross-checked by an Experienced Post Graduate Supervisor (EPGS) blinded to treatment allocation group. Those teeth with width of the cavity preparation were no more than 1/3rd of the inter-cuspal width were included. Radiographs (Durr PSP Sensor, Durr, Germany) are taken to assess the depth of the

preparation and Remaining Dentin Thickness (RDT). Two RDT measurements from mesial and distal pulp horn to floor of the preparation were calculated. Mean RDT was derived from the two readings. Radiograph assessment was done by EPGS. Teeth were excluded from the study if they had pulp exposure or a prepared cavity that did not meet standardization requirements.

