Post –operative sensitivity after 24 and 48 hours were assessed with VAS score (1- 10) through telephonic call by a resident student who are unaware of the treatment allocation group. The Visual Analogue Scale (VAS) is a common and effective tool for assessing pain and other subjective symptoms, including postoperative sensitivity. In this study a 1-10 scale were used and the patient is asked to choose a number ranging from 1 to 10 based on their sensitivity, with 1 being the least sensitivity and 10 being the most. The advantages of VAS scale is its simplicity, ease of use and applicability.

Post-operative sensitivity after one week all the patients were recalled and clinically assessed by Schiff cold air sensitivity scale by an Experienced Post Graduate Supervisor (EPGS) who is unaware of the allocated treatment groups and those patients with post-operative sensitivity of VAS > 3 were considered for the results (Berkowitz G *et al* 2013)¹¹. A statistician also looked at the treatment results without knowing anything about them.

Schiff cold air sensitivity scale is used to check for post-operative sensitivity which measures a patient's response to a cold air stimulus, helping to gauge the level of sensitivity in a tooth. The procedure involves directing a stream of air at the tooth and observing the patient's reaction, with scores ranging from no response to severe pain (intensity) requiring immediate discontinuation of the stimulus.

The secondary outcome was to assess whether patient had post-operative sensitivity due to any trigger stimulus. This was assessed at the end of 24 hours, 48 hours and one week post-operatively. At 24 hours and 48 hours through telephonic call a resident student who is unaware of the treatment allocation group questioned the patients those who had post-operative sensitivity whether the sensitivity is due to any stimuli (upon mastication/ intake of hot or cold) or spontaneous.

At the end of one week the patients were recalled checked for post-operative sensitivity using both Schiff Air Scale and those patients with post-operative sensitivity of VAS > 3 were questioned whether sensitivity is due to any stimuli¹¹ (upon mastication/ intake of hot or cold) or spontaneous.

STATISTICAL ANALYSIS PLAN

DEFINITION:

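### The unit of analysis is inconsistent: 504 restorations are planned, patients are randomised, and the rank tables imply 252 analysed values, which bears on the printed Ns and the 1-week limit

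*Combined protocol and SAP*

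**What the plan says.** **Size.** The Brief Summary, the Detailed Description and the SAP (Sample Size Calculation) all state that "a sample size of 504 restorations was calculated to be sufficient for detecting statistical difference", obtained "using G* power software (α probability error – 0.05 and effect size – 0.2". The Brief Summary splits this as "Arms (n=84 in each". No power is stated.

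**Allocation.** Under Sample Size, Blinding and Randomization the unit is the patient: "All patients were allocated using Block randomization", "patients who met the eligibility criteria were systematically assigned in a continuous fashion", and "After every 6th patient, the enrolment would continue on to the next block from 1". Exclusion after cavity preparation is by tooth (Materials and Methodology).

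**Outcome.** For the 24- and 48-hour calls, "the patient is asked to choose a number ranging from 1 to 10 based on their sensitivity". The text does not say whether this is once per patient or once per tooth. At one week the patient is recalled and cold air is directed at the tooth (Outcome measures).

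**Analysis.** The SAP uses Kruskal-Wallis at each time point and Mann-Whitney for the two control arms. Its own Definition section describes Kruskal-Wallis as a test for independent groups. No clustering term appears.

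**Not given.** There is no patient count, one-restoration rule, index-tooth rule or number of restorations per patient. The N columns of the two Ranks tables carry no unit; they total 504 and 168.

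**The concern.** Size is counted in one unit and allocation in another, and nothing links the two. If each patient has one restoration, the difference is only one of wording. If some have two, those restorations share one allocation and one mouth, and perhaps one telephone score, so they are not two independent observations. The sample-size calculation, the rank tests and the 1-week confidence limit all need a count of independent units, and the plan never says what that count is.

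The SAP's tables show that the gap matters. The number of values that were ranked and the number printed beside them differ by a factor of two. At stake are the meaning of 504, every N in the tables, and the one comparison that is reported with a confidence limit.

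**Working it through.** **1. Reproducing 504.** Inputs from the plan: "α probability error – 0.05 and effect size – 0.2" and six arms. Assumptions: 0.2 is Cohen's f, and the calculation is the omnibus one-way ANOVA with noncentrality λ = N·f². For N = 504, λ = 504 × 0.04 = 20.16 on 5 and 498 df, and power is 0.952. The smallest N reaching 0.95 is 501, which rounds up to 504 (6 × 84). Powers of 0.80 and 0.90 would give 330 and 420. So 504 fits a target of 0.95 with 504 independent units. That target is inferred; a chi-square calculation with w = 0.2, 5 df and power 0.95 gives 495, which is also close.

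**2. How many values were ranked.** The average of n ranks is (n + 1)/2, with or without ties. The N-weighted average of the arm mean ranks therefore returns n, and doubling or halving every arm N leaves that average unchanged.

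Pre-operative: (86 × 105.48 + 94 × 141.70 + 86 × 116.12 + 82 × 142.30 + 80 × 106.20 + 76 × 147.55)/504 = 63,755.8/504 = 126.50.

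| Table block | Weighted mean rank | Implied n = 2 × mean − 1 | Printed N |
|---|---|---|---|
| Pre-operative, six arms | 126.50 | 252 | 504 |
| 24 h, six arms | 126.50 | 252 | 504 |
| 48 h, six arms | 126.50 | 252 | 504 |
| 1 week, six arms | 126.50 | 252 | 504 |
| Pre-operative, two controls | 42.50 | 84 | 168 |
| 24 h, two controls | 42.50 | 84 | 168 |

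With 504 ranked values the average would be (504 + 1)/2 = 252.5. The blank self-etch control cell at 48 h is taken as 82, as in the other blocks. The 84 in the control comparison covers both control arms together (43 + 41); it is not the 84 planned per arm.

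**3. Cross-checks on 252.**
- Every printed N is even. Halved, they are 43, 47, 43, 41, 40 and 38, total 252.
- If scores are whole numbers, all 24 means in the SAP's table of mean scores are attainable with the halved Ns (for example 37/43 = 0.86 and 77/41 = 1.88).
- Pre-operative Kruskal-Wallis without tie correction, with n = 252 and the halved Ns: H = [12/(252 × 253)] × Σ nᵢ(R̄ᵢ − 126.5)² = 14.69, p = 0.012. The printed p = 0.003 corresponds to H = 17.96 on 5 df, so a tie factor of 14.69/17.96 = 0.82 reconciles them. Had each value been entered twice, H would have roughly doubled and p would be far below 0.003.

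**4. The 1-week limit.** Inputs from the SAP: means 0.26 and 0.08 (difference 0.18), SDs 0.95 and 0.27, and a one-sided 95% limit. SE = √(0.95²/n₁ + 0.27²/n₂); limit = 0.18 − 1.645 × SE.

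| n₁, n₂ | SE | Lower limit |
|---|---|---|
| 84, 84 (planned) | 0.1078 | +0.003 |
| 86, 80 (printed) | 0.1068 | +0.004 |
| 43, 40 (implied by the ranks) | 0.151 | −0.068 |

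The reported 0.1077 and +0.003 match 84 per arm. On the number of values ranked, the limit changes sign.

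**5. What clustering would cost, if there is any.** The documents give neither restorations per patient (m) nor the within-patient correlation (ICC), so only a range can be shown. Design effect = 1 + (m − 1) × ICC; effective N = 504/design effect; power as in step 1.

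| m | ICC | Design effect | Effective N | Power |
|---|---|---|---|---|
| 1 | any | 1 | 504 | 0.952 |
| 1.25 | 0.3 | 1.075 | 469 | 0.935 |
| 1.5 | 0.5 | 1.25 | 403 | 0.888 |
| 2 | 0.5 | 1.5 | 336 | 0.814 |
| 2 | 1 | 2 | 252 | 0.670 |

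These powers come from the ANOVA formula and are approximate for rank tests.

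**The case against.** The strongest reply is that nothing shows a breach of independence. No section says that any patient received more than one restoration, and the text on allocation and assessment fits one per patient. The telephone score is not said to be asked once per patient, and the N columns are not said to count restorations. The rank tests were not run on 504 values at all. If the 252 ranked values are 252 patients, the rank tests respected independence. The documents also claim no power, so there is no stated figure from which power can be said to have fallen.

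All of that stands, and it rules out a stronger reading. A reader might infer that the Kruskal-Wallis and Mann-Whitney tests treated correlated restorations as independent, so that their error rate is well above 5%. That figure would be about 19% to 35% for two restorations per patient with ICC 0.5 to 1, but only if 504 such values had been ranked. The mean ranks show that they were not. The upper figure also needs every patient to have two teeth with identical scores, which cannot simply be carried over to the one-week clinical test on the tooth.

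The reply does not supply the missing patient count, does not explain why printed N and ranked n differ by a factor of two, and does not touch the 1-week limit.

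**Conclusion.** The point holds as an inconsistency in the unit of analysis. It rests on arithmetic from the printed tables: 252 values ranked against a printed 504, and 84 against 168. Two explanations fit: 252 patients with two restorations each, with ranks by patient and N by restoration; or an N column that was simply doubled. A reader might favour one of them, but the documents cannot decide. Correlation between restorations remains a risk, and inflation of the rank tests' error rate is not shown.

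The consequence that can be shown is for the stated 504, the printed Ns and the 1-week comparison, where the SE rises from 0.108 to 0.151 and the lower limit moves from +0.003 to −0.068 if 43 and 40 are the true counts. If 0.2 is Cohen's f for six groups, power is 0.95 with 504 independent units and 0.67 with 252. If each of 504 patients had one restoration and all were analysed, nothing would be lost, but the rank tables would then need another explanation.

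**What to change.** 1. Report the numbers of patients and of restorations in each arm.
2. Restate 504 in the independent unit actually analysed, with its power and the type of effect size. Put every N in that unit, label it, and reconcile the N columns with the mean ranks.
3. Recompute the 1-week SE and lower limit on that unit.
4. If any patient contributed more than one restoration, analyse one value per patient, from an index tooth chosen by a rule that does not depend on outcome. Alternatively keep all teeth in a GEE or mixed ordinal model clustered on patient, in place of the rank tests.

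The cost is revised SAP wording, a count from the existing records and one re-run. The downside is a smaller stated N and a wider 1-week interval, if 252 proves to be the number of independent units.

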5% of Glutaraldehyde component acts as a biological fixative, essentially coagulating proteins within the dentinal tubules and causing them to become blocked. This prevents the movement of fluid within the tubules, which is a primary cause of dentin hypersensitivity. 35% of HEMA is a hydrophilic monomer that also contributes to the occlusion of dentinal tubules. It enhances the penetration of the solution into the tubules and helps to further block the fluid flow. The mechanism of Gluma desensitizer is both the glutaraldehyde and HEMA work together to reduce the permeability of the dentin, thus minimizing the stimuli that trigger sensitivity.

In this clinical trial the numbers of arms were randomly assigned to six groups. Blinding helps to ensure that the results of the study are more reliable and less influenced by the subjective opinions or expectations of the participants or researchers. Hence in this clinical trial, single-blinding was done. The participants of the study were informed about the trial but were unaware of which treatment group they were allocated to. The clinician and researcher were aware of the groups and treatments given. This blinding was also done to minimize bias that could arise from the patient's expectations or perceptions about the treatment. In this clinical trial all the patients were allocated using Block randomization, a technique which is used to ensure balance in treatment group sizes throughout the trial. It works by dividing participants into individual blocks

and then randomly assigning treatments within each block, ensuring roughly equal numbers in each group within that block¹⁰. In this clinical trial, a block size of 6 (1, 2, 3, 4, 5, 6) was employed for equal enrolment. The prepared blocks were printed in sheets and patients who met the eligibility criteria were systematically assigned in a continuous fashion. After every 6th patient, the enrolment would continue on to the next block from 1.

Arm Title

Arm 1: Total Etch Control group (No desensitizer application) (n=84)

Arm 2: Total Etch Gluma prior to acid etchant usage (n=84)

Arm 3: Total Etch Gluma desensitizer application after acid etchant usage (n=84)

Arm 4: Self Etch Control group (No desensitizer application) (n=84)

Arm 5: Self Etch Gluma desensitizer application prior to etching (n=84)

Arm 6: Self Etch Gluma desensitizer application after self-etch adhesive usage (n=84)

Arm information and description:

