All statistical analyses were performed using non-parametric tests due to the non-normal distribution of the data, as confirmed by both the **Kolmogorov–Smirnov** and **Shapiro–Wilk** tests

($p < 0.001$). Descriptive statistics including mean and standard deviation (Mean \pm SD) were calculated for each of the six desensitizer groups at different time points: Pre-operative, 24 hours, 48 hours, and 1 week post-operative sensitivity, measured using the Visual Analog Scale (VAS).

For intergroup comparisons across all six desensitizer protocols, the **Kruskal–Wallis test** was used independently for each time point. This non-parametric method was selected to assess statistically significant differences in median VAS ranks among the groups, given the violation of normality assumptions. A separate p -value was generated for each time point:

- Pre-operative VAS: $p = 0.003$ (significant)
- 24-hour VAS: $p = 0.126$ (not significant)
- 48-hour VAS: $p = 0.050$ (borderline)
- 1-week VAS: $p = 0.013$ (significant)

Pairwise comparisons between the **Total-etch control** and **Self-etch control** groups were performed using the **Mann–Whitney U test**. This analysis revealed a statistically significant difference in pre-operative VAS scores ($p = 0.012$), while post-operative scores showed no significant differences at 24 hours ($p = 0.337$).

Mean pain scores (VAS) were also summarized for each group at all four-time intervals. The **self-etch Gluma prior to etching group consistently showed the lowest VAS scores** at all time points, suggesting reduced post-operative sensitivity in this group.

Given the minimal differences in outcome scores among the other groups, and the slightly better performance of the self-etch GLUMA prior to etching group, the data suggest that **most treatment protocols were non-inferior** to the best-performing group. Therefore, the trial was interpreted as

a **non-inferiority study**, evaluating whether the other etching and desensitizing protocols were not clinically worse than the most effective group.

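### The allocation rule contradicts itself and no concealment is described; the arms differ in pre-operative VAS and no test adjusts for it

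*Combined protocol and SAP*

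**What the plan says.** The Brief Summary (Sample Size, Blinding and Randomization) and the Detailed Description give the same account of allocation. The general statement is "It works by dividing participants into individual blocks and then randomly assigning treatments within each block". The operating details read differently. Blocks have six places, numbered 1 to 6, one for each arm. The rule for using them is "The prepared blocks were printed in sheets and patients who met the eligibility criteria were systematically assigned in a continuous fashion". On what happens once a block is full, both sections add "After every 6th patient, the enrolment would continue on to the next block from 1". On blinding, they say "The clinician and researcher were aware of the groups and treatments given". Planned arms are 84 each.

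Neither section names a method of generating the sequence, a holder of it, or any form of concealment. Eligibility depends partly on the finished preparation: "Teeth were excluded from the study if they had pulp exposure or a prepared cavity that did not meet standardization requirements". When this check took place relative to assignment is not stated.

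The SAP's Procedure section compares VAS across the six arms with a separate Kruskal-Wallis test at each time point and compares the two controls with Mann-Whitney tests. It reports pre-operative p = 0.003 across the six arms and p = 0.012 between the controls. It then identifies self-etch Gluma prior to etching as having the lowest VAS at every time point and reads this as reduced sensitivity. No analysis adjusts for the pre-operative score.

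**The concern.** Random order within blocks and systematic assignment restarting from 1 are different procedures, and the first gives a randomised trial while the second may not. With no concealment described, a block size fixed at the number of arms, and study staff who knew the groups, the next assignment was at least partly predictable.

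The consequence that can be seen in the data is at baseline. The arms were not alike before treatment, and the arm credited with the best result had the lowest mean at the start. An unadjusted comparison of post-operative scores cannot separate a treatment effect from that head start. The SAP's main descriptive conclusion rests on such a comparison.

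**Working it through.** **1. Predictability.** The inputs are six arms, a fixed block of six and one slot per arm.
- Fixed order 1 to 6, or a visible list: every next assignment is known (100%).
- Permuted order, list hidden, past assignments known: expected correct guesses per block are 1/6 + 1/5 + 1/4 + 1/3 + 1/2 + 1 = 2.45. As a share, 2.45/6 = 40.8%, against 1/6 = 16.7% by chance. The last place in each block is certain. That is 504/6 = 84 assignments if each patient contributed one restoration, which the documents do not state.

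**2. Arm sizes.** Complete blocks of six over 504 units give 504/6 = 84 per arm, in rotation or permuted. The rank table prints 86, 94, 86, 82, 80 and 76 (sum 504), which depart from 84 by +2, +10, +2, −2, −4 and −8. One incomplete block can separate two arms by at most 1; the observed range is 18.

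**3. Is the printed pre-operative p = 0.003 credible?** The inputs are the mean ranks in the six-arm table: 105.48, 141.70, 116.12, 142.30, 106.20, 147.55.
- Their average weighted by the printed Ns is 63,755.8/504 = 126.5. Ranks of N units average (N + 1)/2, so N = 252. For 504 units the average would be 252.5.
- I therefore halved the Ns: 43, 47, 43, 41, 40, 38.
- H = 12/[N(N + 1)] × Σ nᵢ(Rᵢ − 126.5)² = 12/(252 × 253) × 78,047.8 = 14.69 on 5 df, p = 0.012 without tie correction.
- The printed p = 0.003 needs H = 17.96, a tie factor of 14.69/17.96 = 0.82. The factor is 1 − (t³ − t)/(N³ − N) for t scores tied at one value. The documents do not give t. Assuming 100, 140 or 160 tied zeros gives p = 0.008, 0.003 or 0.001.
- Cross-check by one-way ANOVA from the printed means and SDs at N = 252: between-arm mean square 72.12/5 = 14.42; within-arm mean square 968.35/246 = 3.94; F = 3.66, p = 0.0032. At N = 504, p is about 1 in a million.

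The baseline difference therefore remains on either count of units. Halving the arms does not rescue the block scheme either: 252/6 = 42, against 38 to 47.

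**4. Does it touch the conclusion?** Mean VAS by arm, from the SAP's table of means:

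| Arm | Pre-op | 24 h | 48 h | 1 week |
|---|---|---|---|---|
| Total etch control | 0.86 | 0.37 | 0.37 | 0.21 |
| Total etch, Gluma prior | 1.72 | 0.49 | 0.40 | 0.23 |
| Total etch, Gluma after | 1.16 | 0.28 | 0.28 | 0.26 |
| Self etch control | 1.88 | 0.66 | 0.41 | 0.12 |
| Self etch, Gluma prior | 0.63 | 0.20 | 0.03 | 0.08 |
| Self etch, Gluma after | 2.11 | 0.61 | 0.37 | 0.21 |

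Self-etch Gluma prior has the lowest mean in every column, including the one before treatment. (By mean rank it is second lowest pre-operatively, 106.20 against 105.48 for total-etch control.) Across the six arms, pre-operative means correlate with later means at r = 0.92 (24 h), 0.72 (48 h) and 0.24 (1 week). With six points this is descriptive only.

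**The case against.** The case on the other side has four parts, and much of it stands.

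- A reader might infer that the treating clinician assigned patients and could steer them. The text is passive and names no assigner. An operator applying Gluma necessarily knows the treatment given, and that is not the same as knowing the next assignment.
- A reader might infer that the sheets were open to view. The documents say only that they were printed. Concealment that is not described is not shown to be absent.
- A reader might take rotation from arm 1 to arm 6 as fact. The digits may be arm labels or slot positions in a shuffled block, and the same paragraph states random assignment. Nor do the analysed arm sizes fit rotation or complete permuted blocks, so the predictability figures describe the scheme as written and not necessarily what was done.
- A reader might take the baseline imbalance as evidence of selection. The pattern is not coherent: controls and Gluma arms lie on both the low and the high side. Chance, departures from the list, or exclusion of prepared teeth could each produce it. The match to 0.003 also depends on an assumed number of ties.

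Patients, the telephone assessor, the one-week assessor and the statistician are described as unaware of allocation. That protects outcome assessment, but it does not protect allocation and does not remove a baseline difference.

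An adjusted analysis chosen now is post hoc, which is a fair objection. It is met by labelling it so and showing the unadjusted tests beside it.

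**Conclusion.** The point holds as a contradiction, an omission and an uncorrected imbalance. The account of allocation is internally inconsistent and describes no concealment. Predictability was between 41% and 100% under the scheme as written; the lower figure assumes permuted blocks, a hidden list and knowledge of past assignments. The analysed arms (76 to 94) did not come from complete blocks of six without departures or exclusions that are not reported.

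Pre-operative VAS differs across arms by up to 2.11 − 0.63 = 1.48 points. The p-value is 0.003 as printed and 0.012 from the printed ranks on 252 units before tie correction. The SAP's inference about self-etch Gluma prior to etching is therefore confounded with baseline, whatever caused the imbalance. The documents do not show selection at enrolment, and this conclusion does not depend on it. Adjustment for pre-operative VAS deals with the measured difference only; it would not restore randomisation if the order proved to be fixed.

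**What to change.** 1. Add a comparison of post-operative scores adjusted for pre-operative VAS, for example a rank-based ANCOVA or a proportional-odds model. Post-operative arm means are only 0.03 to 0.66, so the proportional-odds model may be unstable, and a fallback should be named before it is run. Base between-arm conclusions on the adjusted result, label it as specified after the results were seen, and report the unadjusted tests beside it. Withdraw the inference drawn from the lowest-scoring arm if it does not survive adjustment.
2. Check the printed sheets. If the order was 1 to 6 in sequence, describe the trial as systematically allocated and not as randomised. If it was permuted, say how it was generated and correct the wording.
3. State who held the sequence, whether it was concealed, when assignment occurred relative to the cavity exclusions, and why arm sizes depart from 84. Give the number of patients as well as restorations, since the ranks fit 252 units and not 504.

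Results are already reported, so no change to block size or concealment procedure is proposed. The cost is an inspection of existing sheets, some rewording and one analysis of data already collected. The downside is a weaker claim of randomisation and an adjusted analysis that must be presented as post hoc.
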